4.2.3 Post Study Follow up and Procedures

Participants will be offered treatment as usual of cognitive rehabilitation or cognitive stimulation should they wish to follow up on cognitive interventions for their MCI.

If the current study results prove to be promising, participants in the active control group will also be offered the VRCT intervention.

4.3 Discontinuation/Withdrawal

4.3.1 Discontinuation Criteria

The study will be discontinued for participants who continuously complain of discomfort and dizziness in using the Virtual Reality equipment.

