1 BACKGROUND AND RATIONALE

As a global public health priority, there has been a pressing demand for the development and deployment of novel interventions to prevent and delay the onset of dementia. In recent years, Computerized Cognitive training (CCT) has garnered considerable evidence in improving the cognitive outcomes of individuals living with Mild Cognitive Impairment (MCI), a transitional stage between normal aging and dementia. The aim of this pilot study is to assess the feasibility and efficacy of CCT, specifically a multi-domain Virtual Reality Cognitive Training (VRCT) program on the cognition of individuals with MCI. The VRCT program will be conducted weekly over a period of 10 weeks for participants aged 65-85 with a diagnosis of MCI. 30 participants will be recruited from specialist outpatient clinics and they will be randomized into either the VRCT intervention group or the active control group. All participants will be assessed at baseline and post-intervention. We hypothesize favorable acceptability of the VRCT program. We also postulate positive changes on neuropsychological measures of attention, processing speed, memory and executive function following program completion. We expect these gains in cognition to be translated to improvements on secondary outcomes including mood and self-reported everyday memory functioning. In CGH, there is currently a lack of follow-up intervention options for patients who have received a diagnosis of MCI. Usual care procedures would include medication for risk factors as well as health advice for lifestyle factors such as exercise, diet and cognitively stimulating activities. If outcomes from this study prove to be positive, it will add to the evidence base of the novel application of Virtual Reality technology to Cognitive Training in a clinical setting. Furthermore, this will provide clinicians in CGH with an innovative intervention option to meet the needs of MCI patients in maintaining and enhancing their cognitive functions.

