3.5 Subject Replacement

Participants who complete at least 8/10 sessions of VRCT will be included in the study. Dropouts will not be replaced.

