4.2.2 Study Visits and Procedures

For Virtual Reality Cognitive Training Intervention Group:

- Visit 1 (Week 1): Pre-intervention neuropsychological testing (2 hours)
- Visit 2-11 (Weeks 2-11): Virtual Reality Cognitive Training (50 minutes per session)
- Final Visit (Week 12): Post-intervention neuropsychological testing (2 hours)

For Active Control Group:

- Visit 1 (Week 1): Pre-intervention neuropsychological testing (2 hours)
- Visit 2 & 3 (5 weeks apart): Psychoeducation and Cognitive Stimulation (1 hour per session)
- Final Visit (Week 12): Post-intervention neuropsychological testing (2 hours)

During the VR session and cognitive training, frequent checks will be performed to ensure that subject is comfortable. Should subject express fatigue or discomfort, session can be stopped and resume when subject is able to continue. The number of breaks will be recorded.

Appointment between sessions will be at least 7 days apart.

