4.3.2 Discontinuation Visit and Procedures

If voluntary withdrawal occurs, participant will be asked to complete the self-report questionnaire to assess intervention acceptability and to collect feedback on the program.

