7.3 Safety Monitoring Plan

The data and safety monitoring would be performed by the principal investigator and co-investigators. The data would be reviewed monthly or at the point of recruitment of every 10 subjects, whichever occurs first. Data that would be reviewed would include adverse events occurring during the intervention such as excessive patient agitation resulting in injuries or device dislodgements requiring termination of intervention.

15 subjects would be receiving intervention. If 8 or more subjects are unable to meet the composite end-point for completion of intervention, the study would be terminated.

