9.2 Statistical and Analytical Plans

Intention-to-treat analyses will be performed using the last observation carried forward method for subjects who were lost to follow-up or had missing data. Data will be analysed using IBM SPSS Statistics 26.0. Continuous variables will be presented as mean and standard deviation (SD) or median and interquartile range (IQR) where appropriate, while categorical variables will be presented as frequencies and percentages. A one-way analysis of variance will be conducted to assess the between-group difference of the intervention's effect over time for each outcome measurement. The significance level will be established at $p < 0.05$. Cohen's d effect size (ES) will be reported alongside the p-values, and thresholds of 0.2 for small, 0.5 for moderate, and 0.8 for large effects were employed as guiding benchmarks.

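### Persistent VR discomfort ends the study rather than VR use, with no week-12 testing requested, so cognitive outcomes can go missing in the VRCT arm only, selected by intolerance

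*Combined protocol and SAP*

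**What the plan says.** Section 4.3.1 gives the plan's only discontinuation criterion: "The study will be discontinued for participants who continuously complain of discomfort and dizziness in using the Virtual Reality equipment." Section 4.3.2, on what happens at discontinuation, deals with voluntary withdrawal only: "If voluntary withdrawal occurs, participant will be asked to complete the self-report questionnaire to assess intervention acceptability and to collect feedback on the program." Neither section mentions cognitive testing.

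Section 4.2.2 schedules testing twice in each group, at week 1 and week 12, so week 12 is the only outcome assessment after baseline. It does not say whether the visit applies to someone already discontinued. Section 1 says in general terms: "All participants will be assessed at baseline and post-intervention." Sections 4.2.2 and 6.3 show that controls receive psychoeducation and cognitive stimulation, without VR.

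Two further statements decide who is analysed. Section 9.2: "Intention-to-treat analyses will be performed using the last observation carried forward method for subjects who were lost to follow-up or had missing data." Section 3.5: "Participants who complete at least 8/10 sessions of VRCT will be included in the study."

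**The concern.** An intention-to-treat comparison needs outcomes from people who stopped the assigned treatment. Followed literally, Section 4.3.1 ends study participation for people who cannot tolerate the headset, and nothing brings them back for the week-12 test. A control participant cannot meet this criterion. The loss therefore falls on one arm, among people selected by their reaction to the intervention.

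Carrying the last observation forward does not repair this. With one post-baseline visit, the last observation is the baseline, so the imputed change is exactly zero. Section 3.5 creates a second problem: people with fewer than 8 sessions may be left out even if they were tested. The two rules give different analysis sets, and their errors need not have the same sign.

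Both primary objectives in Section 2.1 are touched. The cognition comparison loses outcomes. If stopping VR also ends the study, device intolerance is also counted as loss from the study, and retention can no longer be separated from adherence. Section 1.2.1 says this pilot is to guide a later randomized trial, which needs both rates.

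**Working it through.** The plan has no power calculation and no figure on this point to reproduce. The check is a side-by-side reading followed by an illustration of size.

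**Reading**

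1. Section 4.3.1 says it is the study that stops. Section 4.2.2 already covers interrupting and resuming a session, so 4.3.1 describes something more final.
2. Section 4.3.2 adds a questionnaire, for voluntary withdrawal only.
3. No section requests week-12 testing after discontinuation, and none forbids it.
4. If the test is missing, Section 9.2 sets change to zero. If Section 3.5 governs, the person is not analysed.

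**Inputs**

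- VRCT arm of 15 (Section 7.3); 15 controls from a total of 30 (Section 9.1).
- k = number who stop. No rate is given. Section 7.3 says: "If 8 or more subjects are unable to meet the composite end-point for completion of intervention, the study would be terminated." Up to 7 non-completers are therefore tolerated, and k = 1, 3, 5, 7 is used (6.7%, 20%, 33.3%, 46.7% of the arm).
- e = 0.35 SD, completers' effect over control. This is the background g in Section 1.2, used only for scale.
- r = retest gain in both arms, assumed to be 0, 0.15 or 0.3 SD. Completers change by e + r and controls by r.
- s = mean change that stoppers would have shown if tested; unknown.

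**Formulas**

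- Truth with everyone tested: (1 − k/15)(e + r) + (k/15)s − r.
- Carried forward: (1 − k/15)(e + r) − r. Error = −(k/15)s.
- Completers only: (e + r) − r = e. Error = (k/15)(e + r − s).

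If stoppers have no benefit, s = r. The carried-forward error is then −(k/15)r, and the completers-only error is (k/15) × 0.35 whatever r is. If stoppers decline by 0.35 SD and r = 0, the carried-forward error is +(k/15) × 0.35.

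| k of 15 | Carried forward, no benefit, r = 0.3 | Carried forward, no benefit, r = 0.15 | Carried forward, decline of 0.35, r = 0 | Completers only, no benefit, any r |
|---|---|---|---|---|
| 1 | −0.02 | −0.01 | +0.02 | +0.02 |
| 3 | −0.06 | −0.03 | +0.07 | +0.07 |
| 5 | −0.10 | −0.05 | +0.12 | +0.12 |
| 7 | −0.14 | −0.07 | +0.16 | +0.16 |

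With no benefit and r = 0, the carried-forward error is zero.

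At the other extreme, suppose all 15 would have had the full 0.35 SD effect, so s = 0.35 + r. Carrying forward then gives 0.28, 0.23 and 0.19 at k = 3, 5 and 7 with r = 0, and 0.24, 0.17 and 0.09 with r = 0.2, against a truth of 0.35.

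**Scale.** Unadjusted standard error with SD 1 and 15 per arm: √(1/15 + 1/15) = √(2/15) = 0.365 SD.

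**Chance that it happens at all.** For assumed stopping rates of 5%, 10% and 20%, 1 − (1 − p)^15 gives a 54%, 79% and 96% chance of at least one stopper among 15.

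**The case against.** The strongest reply is that the plan is silent rather than wrong. One loosely drafted sentence may have been meant to stop the VR sessions only. Section 1 says everyone is assessed after the intervention, Section 4.2.2 attaches no completion condition to the final visit, and Section 9.2 commits to intention to treat. Testing after stopping VR is therefore an available reading. That is fair, and the point here is only that the plan does not ask for the test. But the specific rule names the study, and the general statements do not address people already discontinued. Staff following the text could reasonably not invite them.

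Second, Section 2.2.1 limits VR use to under 30 minutes with regular comfort checks, Section 4.2.2 allows breaks, and the criterion requires continuous complaint. These should reduce the number affected. They do not change what happens to those who are affected.

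Third, the size is almost wholly assumed. The upper limit of 7 comes from a rule on all-cause non-completion whose composite end-point is not defined, so it is a loose ceiling for discomfort alone. The result also depends on what stoppers would have scored, as the extreme cases above show. This stands: the figures are illustrative, and the sign cannot be known if these people are not tested.

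Fourth, the conflict between Sections 3.5 and 9.2 exists whatever Section 4.3.1 says. That is true. It is treated here because it affects the same people, and testing them achieves little if they are then left out.

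**Conclusion.** The concern holds. As written, the plan can lose the only post-baseline cognitive outcome in the VRCT arm alone, through intolerance of the intervention, and neither rule for handling these people restores the intention-to-treat comparison. The conflict between Sections 3.5 and 9.2 is an error as written; the rest is an inexpensive improvement that should be made.

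In the main illustrations the effect is understated by at most 0.14 SD or overstated by at most 0.16 SD. Both maxima need 7 of 15 to stop; with 1 to 3 stopping, the errors are 0.07 SD or less. These figures rest on assumed stopping numbers, retest gains and stopper outcomes, and on the background 0.35 SD. They are under half of the 0.37 SD standard error and would be hard to see in an unpowered pilot of 30. They are systematic, however, and would carry into the planning of the later trial.

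**What to change.** - In Sections 4.3.1 and 4.3.2, distinguish a participant who stops VR sessions from one who withdraws from the study. The criterion for stopping VR is left as it is.
- Ask every randomized participant who has not withdrawn consent to follow-up, including those who stop VR for discomfort, to attend the scheduled week-12 testing with the blinded assessor.
- Report by arm how many stopped sessions and how many withdrew from the study.
- Reconcile Section 3.5 with Section 9.2, so that everyone tested is analysed in the randomized arm and 8 of 10 sessions describes adherence instead of deciding inclusion.

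The cost is wording in Sections 3.5, 4.3.1, 4.3.2 and 9.2, and a check that the consent form, not seen here, agrees. The 2-hour visit and the assessor are already in the plan. Some participants may still decline, so some missing data will remain.

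Section 16 already summarizes results. If data collection is over, the request for testing can apply only to the follow-on trial. Reporting by arm who stopped VR, who was tested and who was analysed, and settling Section 3.5 against Section 9.2, can still be done for this one.

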4.3.2 Discontinuation Visit and Procedures

If voluntary withdrawal occurs, participant will be asked to complete the self-report questionnaire to assess intervention acceptability and to collect feedback on the program.

5 TRIAL MATERIALS

5.1 Trial Product (s)

Virtual Reality (VR) System

The VR experiences are administered through a head-mounted Oculus Go Screen V7. The hardware specifications are as follows:

- Oculus Go Screen: 5.5-inch display with a 2560 x 1440 resolution (1280 x 1440 per eye)
- Oculus Go Processor: Qualcomm's Snapdragon 821 processor from

- Oculus Go Weight: 468 grams

The VR system runs on a software developed by Dancing Mind Pte Ltd. The software specifications and service provided by Dancing Mind Pte Ltd include:

- MindGym System Functions: System Setup (Processor Setup, Password Changing etc)
- Data Centre (Memory Care Therapy Data Analytics Report Querying and Printing Functions)

To ensure infection control, all equipment will be sanitized with alcohol wipes after use.

6 TREATMENT

6.1 Rationale for Selection of Dose

The VRCT Program

Participants will undergo 50 minutes of weekly VRCT sessions over an 10-week intervention period. The program consists of three components: (1) psychoeducation on cognitive functioning and ways to maintain cognitive health, (2) VR cognitive training tasks and (3) VR relaxation modules. The cognitive training tasks are designed to target cognitive performance on domains including attention, working memory, memory and executive functions. These tasks require participants to: (1) remember placement and order of pictures in a specific timeframe, (2) identify and recall commonly seen objects, (3) identify 3D moving objects without being distracted by messages, (4) strategize route to escape a maze under time constraints etc. Psychologists who are conducting the program will monitor participants' individual progress. Task difficulty is continuously adjusted based on participants' performance. The VR relaxation modules consist of mindfulness and meditation activities designed to enhance mental well-being.

6.2 Blinding

Participants will be informed in the participant information sheet that if they were to agree to participate in the study, they will be randomized either to the VRCT group or active control group.

6.3 Concomitant therapy

Participants assigned to the active control group will undergo two hourly sessions of psychoeducation on cognitive health and cognitive stimulation activities. They will also be given a cognitive stimulation kit consisting of puzzles and games and provided with a weekly guide to engage in these intellectual activities weekly at home.

7 SAFETY MEASUREMENTS

7.1 Definitions

An adverse event (AE) is any untoward medical occurrence in a patient or clinical investigation subject administered a pharmaceutical product and which does not necessarily have a causal relationship with this treatment. An adverse event (AE) can therefore be any unfavourable and unintended sign (including an abnormal laboratory finding), symptom, or disease temporally associated with the use of a medicinal (investigational) product, whether or not related to the medicinal (investigational) product.

A serious adverse event (SAE) is any untoward medical occurrence that at any dose:

- results in death
- is life-threatening
- requires inpatient hospitalisation or prolongation of existing hospitalisation
- results in persistent or significant disability/incapacity, or
- is a congenital anomaly/birth defect

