2.2.1 Potential Risks

The use of VR equipment for an extended period of time may induce a dizzy feeling in older adults. In order to prevent this, we limit the duration of VR usage to under 30 minutes. We will also check in with our participants in regular intervals to assess their comfort levels. Participants with severe visual or hearing impairment will be excluded from this study.

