7.2 Collecting, Recording and Reporting of Serious Adverse Events (SAEs) to CIRB

Only related SAEs (definitely/ probably/ possibly) will be reported to CIRB. Related means there is a reasonable possibility that the event may have been caused by participation in the clinical trial. Please refer to the CIRB website for more information on Reporting Requirement and Timeline for Serious Adverse Events.

The investigator is responsible for informing CIRB after first knowledge that the case qualifies for reporting. Follow-up information will be actively sought and submitted as it becomes available.

Related AEs will not be reported to CIRB. However, the investigator is responsible to keep record of such AEs cases at the Study Site File.

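### The adverse event definition is drug-trial text that does not clearly cover the headset and does not cover the control arm, and no section requires dizziness to be counted

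*Combined protocol and SAP*

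**What the plan says.** Section 7.1 defines an AE as an untoward event in a patient or "clinical investigation subject administered a pharmaceutical product". Its second sentence widens this to unfavourable signs, symptoms or disease, but only those "temporally associated with the use of a medicinal (investigational) product, whether or not related to the medicinal (investigational) product". The serious AE definition that follows has no such product limit.

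The trial product in Section 5.1 is a device and its software: "The VR experiences are administered through a head-mounted Oculus Go Screen V7". Under Section 6.3 the controls receive two sessions of psychoeducation and stimulation activities and a kit to use at home.

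On harms, Section 2.2.1 says that extended VR use "may induce a dizzy feeling in older adults", and it answers this with a time limit on VR use and regular comfort checks. Section 4.2.2 repeats the checks and adds: "The number of breaks will be recorded". Section 4.3.1 discontinues participants whose complaints of discomfort and dizziness are continuous. Section 7.3 reviews AEs during the intervention, with these examples: "excessive patient agitation resulting in injuries or device dislodgements requiring termination of intervention". Under Section 7.2 related AEs are not sent to the review board, but "the investigator is responsible to keep record of such AEs cases at the Study Site File". Section 8.1 says more generally that AEs and serious AEs will be recorded and monitored. Section 9.2 describes no tabulation of AEs.

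**The concern.** The AE definition is an operative rule. The recording duties in 7.2 and 8.1 and the review in 7.3 all use the term that 7.1 defines. A definition built around a medicine leaves staff to decide for themselves whether an event in a headset session counts, and gives them no basis for deciding about an event in a control participant.

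The symptom most at risk of being lost is the one that the protocol itself expects. This is a feasibility study of a headset in people aged 65 to 85, and retention and adherence are the first primary objective in Section 2.1. Dizziness bears directly on both. If mild or passing dizziness is not recorded, the team planning the later randomised trial cannot tell whether it was absent or simply not written down.

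**Working it through.** The plan states no AE rate or safety precision, so there is no figure to reproduce. The check is mainly a comparison of the text, with one interval and one count of contacts.

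**1. Does the 7.1 definition fit the trial?**
- First sentence: requires a pharmaceutical product. Neither arm receives one (5.1, 6.3).
- Second sentence: requires use of a medicinal (investigational) product. Because 5.1 lists the VR system as the trial product, a lenient reader could stretch this to the headset. The controls use no trial product, so no reading of this sentence covers them.
- Section 7.2 judges relatedness by participation in the trial, not by exposure to a product. Sections 7.1 and 7.2 therefore use different frames.

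**2. Does any section require dizziness to be counted?**

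| Section | What it provides | What it leaves out |
|---|---|---|
| 2.2.1 | Comfort checks | Recording of their result |
| 4.2.2 | Comfort checks; number of breaks | Reason for each break |
| 4.3.1 | Discontinuation for continuous complaints | Transient complaints |
| 4.3.2 | Acceptability questionnaire on voluntary withdrawal | Anyone who does not withdraw |
| 7.2 | File record of related AEs | Events judged unrelated; depends on 7.1 |
| 7.3 | Review of AEs, open list of examples | Dizziness is not named |
| 8.1 | AEs recorded and monitored | Depends on 7.1; no solicited symptom |
| 9.2 | Efficacy analysis | Any AE table |

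An episode that passes without a break leaves no required trace unless staff choose to call it an AE. An episode that causes a break leaves a count without a cause.

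**3. How much could 15 exposed people show with complete recording?** Section 7.3 gives 15 receiving the intervention. With 0 events, the exact (Clopper-Pearson) upper 95% limit is 1 − 0.025^(1/15) = 1 − 0.782 = 0.218, so the interval is 0% to 21.8%. The count of 0 is an illustration, not a documented result. The interval shows the precision available from 15 people. It does not measure the flaw, and it would be the same after the fix.

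**4. Could the arms be compared?** Under 4.2.2 the VR arm has 10 intervention sessions and the controls have 2, a ratio of 10/2 = 5. If dizziness were asked about at each VR session only, there would be up to 10 occasions of asking in one arm and none in the other. A difference between arms would then partly reflect how often people were asked.

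**The case against.** The strongest reply is that the protocol should be read as a whole. Section 8.1 requires AEs to be recorded with no limit to related events or to one arm. Section 7.3 speaks of AEs during the intervention and gives device dislodgement as an example, so the authors clearly apply the term to headset sessions. The serious AE definition has no product restriction. All of this stands. A reader might infer from 7.1 that none of the 30 participants could ever have an AE; the documents do not support that as the working meaning.

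A reader might also infer that 7.3 shuts dizziness out of the safety review. It does not: its list is introduced as examples. Nor is dizziness the only discomfort or harm in the protocol, since fatigue, discomfort, agitation with injury and dislodgement appear elsewhere. It is the only one named in 2.2.1.

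It is also fair to say that an AE rate is not among the stated objectives and that dizziness is partly handled through checks, breaks and discontinuation.

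What the reply does not remove is narrower. Section 8.1 still relies on a term whose definition does not fit the trial, the controls remain outside that definition, and no section turns the comfort checks into a count.

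**Conclusion.** The concern holds in this limited form. The AE definition is mismatched to the trial: it covers the headset only by a generous reading, and it does not cover the control arm. The gap concerns non-serious events. No section requires dizziness to be counted, so transient dizziness can go unrecorded in a study where tolerability bears on retention and adherence.

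The size of the loss is unknown, because nothing in the documents gives a rate of dizziness or of under-recording. It would be wrong to say that most of the safety information is lost. The Results Summary in Section 16 gives cognitive outcomes and no AE or dizziness count. That does not show that events were missed, but from this document a reader cannot tell none occurred from none counted.

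The conclusion assumes that no session form or manual outside this document already records dizziness or the reasons for breaks. It should be corrected, but it does not undermine the trial's main comparisons.

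**What to change.** - **7.1:** define an AE as any unfavourable medical event in a participant of either arm, from consent to the final visit, whether or not related to study procedures.
- **7.3:** name dizziness and discomfort among the events reviewed.
- **4.2.2:** at each VR session record dizziness or discomfort (yes/no) and the reason for each break. Staff already make the checks.
- **9.2:** report the proportion with dizziness in the VR arm descriptively, with an exact 95% confidence interval. Compare AEs between arms only where they are ascertained the same way in both, for example by the same question at the final visit.

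The cost is protocol wording and one extra line on the session form, plus one question at the final visit if arms are to be compared. There are no new visits. The reported AE count may rise because more is being asked.

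New wording cannot recover events that were not recorded. As Section 16 already holds results, the sponsor should also report the breaks, discontinuations and AEs that were recorded, and say how AEs were ascertained. The corrected definition should carry into the planned follow-on trial.
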